
Criteria for Evaluation: Efficacy
	
The primary efficacy endpoint is the:
 
 1. Proportion of subjects receiving PTG-100 with clinical remission at Week 12 compared with placebo 
Clinical remission is defined as follows, using the Mayo subscores of stool frequency, rectal bleeding, and endoscopy:
 
 • Stool frequency subscore of 0 or 1 with a pre-specified change of 1 or more from baseline • Rectal bleeding subscore of 0 • Endoscopy subscore of 0 or 1 (modified so that a score of 1 does not include friability) 
The secondary efficacy endpoints (all based on comparison of individual PTG-100 dose levels to placebo) are:
 
 1. Proportion of subjects with endoscopic response at Week 12 (Day 84) (defined as an endoscopic subscore of 0 or 1) 2. Proportion of subjects with clinical response at Week 12 (Day 84) (defined as at least 1 point and 30% reduction from baseline in rectal

	
bleeding and stool frequency subscores)
 
 3. Mean change in endoscopy subscore from baseline to Week 12 4. Mean change in rectal bleeding and stool frequency subscores from baseline to Weeks 2, 4, 6, 8, 10, 12, and 16 (Days 14, 28, 42, 56, 70, 84, and 112) 5. Proportion of subjects with endoscopic remission at Week 12 (Day 84) (defined as an endoscopic subscore of 0) 6. Mean change in complete Mayo Score (including all 4 subscores) from baseline to Week 12 (Day 84) 7. Mean change in partial Mayo Score (excluding endoscopy subscore) from baseline to Weeks 2, 4, 6, 8, 10, 12, and 16 (Days 14, 28, 42, 56, 70, 84, and 112) 8. Mean change in faecal calprotectin levels from baseline to Weeks 6 (Day 42), 12 (Day 84), and 16 (Day 112) 9. Mean change in IBDQ score from baseline to Week 12 (Day 84) 10. Proportion of subjects developing ADA by Weeks 12 (Day 84) and 16 (Day 112) 
The exploratory efficacy endpoints (all based on comparison of individual PTG-100 dose levels to placebo) are:
 
 1. Mean change in histological score from baseline to Week 12 (Day 84) 2. Effects of ADA on PK, safety, and efficacy in subjects with positive ADA

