3 STUDY OBJECTIVES

The primary objectives of this study are:

1. To evaluate the safety and tolerability of PTG-100
2. To evaluate the efficacy of PTG-100 in the induction treatment of subjects with moderate to severe active UC compared to placebo.

The secondary objectives are:

1. To evaluate the dose-response relationship and select PTG-100 induction regimens for continued development
2. To evaluate the PK of PTG-100 in subjects with active UC

3. To evaluate the PD effects of PTG-100 including the assessment of RO and $\alpha 4\beta 7$ RE in peripheral blood lymphocytes
4. To evaluate changes in faecal calprotectin levels for subjects receiving PTG-100 compared to placebo
5. To evaluate the incidence of positive ADAs in subjects receiving PTG-100.

The exploratory objectives are:

1. To evaluate the ability of subjects receiving PTG-100 to achieve histological improvement in colonic tissue biopsies compared to placebo
2. To characterise immunologic biomarkers in the target population and to evaluate changes in immunological/PD biomarkers in subjects receiving PTG-100 compared to placebo

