6.12.3 Anti-drug Antibody Blood Sample Collection and Processing

Blood samples (3 mL) will be collected in heparinised blood collection tubes according to the study schedule ([Table 6-1](#)) and serum will be evaluated for the presence of ADAs with a bridging immunoassay.

The Sponsor will supply complete written instructions for the collection, handling, processing, storage, and shipping of samples in the laboratory manual.

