7.8 Immunogenicity Analysis

The proportion of subjects developing ADA by Weeks 12 (Day 84) and 16 (Day 112) will be characterised.

Serum samples will be evaluated for the presence of ADA through use of a validated bridging immunoassay. This will involve conjugating PTG-100 to biotin or horseradish peroxidase (HRP) enzyme using a flexible PEG linker. The biotin conjugate will be used to immobilize PTG-100 to streptavidin coated wells of assay plates. Clinical serum samples containing anti-PTG-100 antibodies will bind to the plate and binding can be detected using horseradish peroxidase-conjugated PTG-100. To validate the ADA assay,

we will spike positive control antibodies into the matrix selected for the assay to measure assay sensitivity and specificity as recommended by the FDA guidance.²⁵ We will also establish a negative control by pooling the sera from 5 to 10 non-exposed individuals. The evaluation will include assessment of neutralizing ADAs, as well as the potential of ADA to cross-react with endogenous MAdCAM-1. If ADA is detected in clinical samples, the effect of ADA on PK, safety, and efficacy may be explored for all subjects who demonstrate evidence of ADAs.

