#### 2.5.3. Pharmacodynamic and Immunogenicity Variables

Quantitation of percent  $\alpha 4\beta 7$  receptor occupancy (%RO) and  $\alpha 4\beta 7$  receptor expression (RE) on peripheral blood T cells will be evaluated as secondary endpoints.

ADA will be categorized as screening, confirmatory, or neutralizing. The proportion of subjects developing neutralizing anti-drug antibodies (ADA) by Week 12 (Day 84) and Week 16 (Day 112) will be evaluated.

Exploratory endpoints will include:

1. Analysis of peripheral blood lymphocytes in subjects on individual PTG-100 dose levels compared to placebo
2. Number of  $\beta 7$  positive cells in colonic biopsies as assessed by immunohistochemistry (IHC) in subjects on individual PTG-100 dose levels compared to placebo
3. Changes in immunologic/PD biomarkers in the target population

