#### 4.6.2. Secondary Efficacy Analyses

Analyses for the secondary endpoints will be conducted using the FAS and PP populations. Where applicable, baseline is defined as the last non-missing pre-treatment assessment prior to initiation of study treatment.

All secondary endpoints that reflect a dichotomous response will be analyzed in the same manner as the primary efficacy endpoint. These secondary endpoints include

- Proportion of subjects with endoscopic response at Week 12 (Day 84) (defined as an endoscopic subscore of 0 or 1)
- Proportion of subjects with clinical response at Week 12 (Day 84) (defined as at least 1 point and 30% reduction from baseline in rectal bleeding and stool frequency subscores)
- Proportion of subjects developing neutralizing antidrug antibodies (ADA)
  - Methods for detection of ADA in clinical samples are presented in Section 7.8 of the protocol
- Proportion of subjects with endoscopic remission at Week 12 (defined as an endoscopic subscore of 0)

Hypothesis testing for all continuous secondary endpoints will be conducted using repeated measures mixed analysis of covariance model adjusted for treatment, time point, treatment-by-time point interaction, stratification factor (TNF-alpha prior use) and baseline values. For subjects who withdraw prematurely, the last observation will be carried forward. These analyses will be based on the Stage 1 and Stage 2 combined data for exploratory purposes. Pairwise comparisons of active drug versus placebo for the change from baseline endpoints will be conducted and p-values derived as described in the analysis of the primary efficacy endpoint. In addition, a summary of observed values and change from baseline values will be presented for each endpoint. Graphical summaries by treatment group of mean change from baseline over time up to Week 12 will also be presented.

Continuous secondary endpoints include

- Mean change in complete Mayo Score (including all four subscores) from baseline to Week 12
- Mean change in Partial Mayo Score (excluding endoscopy subscore) from baseline to Weeks 2, 4, 6, 8, 10, 12, and 16 (Days 14, 28, 42, 56, 70, 84, and 112)
- Mean change in endoscopy subscore from baseline to Week 12 (Day 84)
- Mean change in rectal bleeding and stool frequency subscores from baseline to Weeks 2, 4, 6, 8, 10, 12, and 16 (Days 14, 28, 42, 56, 70, 84, and 112)
- Mean change in fecal calprotectin levels from baseline to Weeks 6 and 12

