Table 14.2.2.7A	Change in IBDQ score from Baseline Over Time (FAS)
Table 14.2.2.7B	Change in IBDQ score from Baseline Over Time (PP)

Table 14.2.2.7C	Change in IBDQ score from Baseline Over Time (Sensitivity Analyses – if Needed)
Table 14.2.2.7A	Change in Histological score from Baseline Over Time (FAS)
Table 14.2.2.7B	Change in Histological score from Baseline Over Time (PP)
Table 14.2.3	Summary of Pharmacokinetic Parameters (PK Population)
Table 14.2.4.1A	Change in $\alpha 4\beta 7$ Receptor Occupancy on Peripheral Blood T cells Over Time (FAS)
Table 14.2.4.1B	Change in $\alpha 4\beta 7$ Receptor Occupancy on Peripheral Blood T cells Over Time (PP)
Table 14.2.4.2A	Summary of $\alpha 4\beta 7$ Receptor Expression on Peripheral Blood T cells Over Time (FAS)
Table 14.2.4.2B	Summary of $\alpha 4\beta 7$ Receptor Expression on Peripheral Blood T cells Over Time (PP)
Table 14.2.4.3A	Change in Peripheral Blood Lymphocytes Over Time (FAS)
Table 14.2.4.3B	Change in Peripheral Blood Lymphocytes Over Time (PP)
Table 14.2.4.4A	Change in $\beta 7$ Positive Cells in Colonic Biopsies Over Time (FAS)
Table 14.2.4.4B	Change in $\beta 7$ Positive Cells in Colonic Biopsies Over Time (PP)
Table 14.2.5.1A	Proportion of Subjects with Positive Neutralizing ADA by Week 12 and Week 16 (FAS)
Table 14.2.5.1B	Proportion of Subjects with Positive Neutralizing ADA by Week 12 and Week 16 (PP)

*Displays of Adverse Events (CSR Section 14.3.1)*

Table 14.3.1.1	Overall Summary of Treatment-Emergent Adverse Events by Treatment Group (Safety)
Table 14.3.1.2	Summary of Treatment-Emergent Adverse Events by System Organ Class, Preferred Term and Treatment Group, Sorted in Descending Frequency according to the Total Column (Safety)

Table 14.3.1.3	Summary of Related/Possibly, Probably and Definitely Related Treatment-Emergent Adverse Events by System Organ Class, Preferred Term and Treatment Group (Safety)
Table 14.3.1.4	Summary of Treatment-Emergent Adverse Events by Severity, System Organ Class, Preferred Term and Treatment Group (Safety)
Table 14.3.1.5	Summary of Treatment-Emergent Serious Adverse Events by System Organ Class, Preferred Term and Treatment Group (Safety)
Table 14.3.1.6	Summary of Most Common ( $\geq 5\%$ within any treatment group) Treatment-Emergent Adverse Events by System Organ Class, Preferred Term and Treatment Group (Safety)
Table 14.3.1.7	Summary of Treatment-Emergent Adverse Events by Preferred Term and Treatment Group (Safety)

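### The protocol's secondary objective is the incidence of positive ADA, but the SAP plans by-arm summaries of neutralising ADA only and declares no change from the protocol

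*SAP*

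**What the plan says.** **Protocol.** Section 3 lists as its fifth secondary objective: "To evaluate the incidence of positive ADAs in subjects receiving PTG-100". The Synopsis carries the matching endpoint, once among the secondary efficacy endpoints and again among the PK/PD/ADA endpoints: "Proportion of subjects developing ADA by Weeks 12 (Day 84) and 16 (Day 112". Section 7.8 repeats it: "The proportion of subjects developing ADA by Weeks 12 (Day 84) and 16 (Day 112) will be characterised". None of these carries a neutralising qualifier. Neutralising antibodies come in separately, as part of the same work: "The evaluation will include assessment of neutralizing ADAs".

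**SAP.** Section 2.5.3 first sorts ADA into three tiers (screening, confirmatory, neutralising) and then names one of them as the quantity to be analysed: "The proportion of subjects developing neutralizing anti-drug antibodies (ADA) by Week 12 (Day 84) and Week 16 (Day 112) will be evaluated". Section 4.6.2 lists the dichotomous secondary endpoints and includes "Proportion of subjects developing neutralizing antidrug antibodies (ADA". In Section 7.1, Table 14.2.5.1A is titled "Proportion of Subjects with Positive Neutralizing ADA by Week 12 and Week 16 (FAS", and Table 14.2.5.1B is its per-protocol counterpart. Section 7.2 has one by-subject immunogenicity listing, 16.2.11. Section 4.6.3 allows a comparison of ADA-positive with ADA-negative subjects if any ADA is detected. Section 5 reports that nothing has changed relative to the protocol analyses.

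**The concern.** A subject with confirmed but non-neutralising antibodies counts toward the protocol's endpoint and toward none of the SAP's ADA tables. The report's planned tables could therefore show few or no positives while the incidence the objective asks about goes unsummarised. This bears on the product's own case: protocol Section 2.1 cites the risk of ADA with existing therapies among the reasons for developing an oral, gut-restricted peptide.

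Two things make it more than loose wording. The restriction recurs in the variable definition, the analysis section and the table shells. And the SAP undertakes in Section 1.2 to set out differences from the protocol, then in Section 5 declares none.

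**Working it through.** No sample size, power or alpha figure is involved, and the plan gives no ADA figure to reproduce. The check is a comparison of texts, followed by one identity for size.

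1. *Quantity required by the protocol.* Section 3, the Synopsis (two places) and Section 7.8 all give the proportion of subjects with ADA, unqualified; the endpoint statements add the Week 12 and Week 16 time points.
2. *Role of neutralising ADA in the protocol.* It is something the ADA evaluation also includes (Synopsis and Section 7.8). It does not define the endpoint.
3. *Quantity analysed by the SAP.* Sections 2.5.3 and 4.6.2 and Tables 14.2.5.1A and B all give the proportion with neutralising ADA. Because Section 2.5.3 separates the three tiers in the sentence immediately before, neutralising cannot be read there as a synonym for positive. Section 4.6.2 refers the reader to protocol Section 7.8 for detection methods, which is the section that states the unqualified endpoint.
4. *Other places where positive ADA could surface in the SAP.* There are two. Listing 16.2.11 gives status subject by subject. The Section 4.6.3 subgroup analysis is worded as optional, depends on ADA being detected, has no shell in Section 7.1, and does not say which tier makes a subject ADA-positive. Neither is a planned summary by arm.
5. *Declaration of changes.* Section 5 says there are none. Steps 1 and 3 show one.

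*Size.* Let A be the proportion of subjects with positive ADA and s the share of those whose antibodies neutralise. On a common set of subjects, the tabulated proportion is

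A × s, with 0 ≤ s ≤ 1.

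The documents give neither A nor s. Taking s over its full range as an assumption: s = 0 gives a tabulated proportion of 0; s = 1 gives A exactly. The planned tables thus give a lower bound on A, and the gap, A × (1 − s), can be anything from zero to the whole of A.

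*Who can be counted.* Under protocol Table 6-1, ADA is sampled at Day 0 predose, Days 28, 56, 84 and 112, and Early Termination. The first scheduled post-baseline ADA sample is Day 28, whereas partial Mayo scoring starts at Day 14. A subject can therefore enter the Full Analysis Set on a Day 14 assessment and leave without a post-baseline ADA result, unless the Early Termination sample is taken. The Safety Population, which requires only some study drug, can contain such subjects too. Any proportion of positives needs a denominator restricted to subjects who had a post-baseline ADA result.

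**The case against.** The strongest defence is that nothing is lost. All three tiers are assigned, individual status is listed, a subgroup analysis would show the number of ADA-positive subjects if it were run, and SAP Section 1.1 lets the sponsor request further analyses. ADA is not among the ten endpoints in the SAP's testing hierarchy or in the numbered list in protocol Section 7.4, and protocol Section 7.8 promises only to characterise it. All of that is correct and limits the consequence. It does not supply a pre-specified by-arm summary of a stated secondary objective, and it does not square with Section 5.

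Three stronger readings are tempting, and the documents do not support them:

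- *That the reported rate is understated.* The tables are labelled as neutralising ADA, and a correctly labelled neutralising rate is not a wrong ADA rate. The protocol's quantity is left unreported, not misreported.
- *That the denominators of the ADA table and the ADA-effect analyses disagree.* SAP Sections 3.1 and 4.6.3 assign the Full Analysis Set and Per Protocol Population to both. What may differ is which subjects count as positive, because Section 4.6.3 leaves its positive group undefined.
- *That immunogenicity should simply move to the Safety Population.* The protocol assigns no population specifically to ADA, and an unrestricted Safety Population denominator would count subjects with no post-baseline sample as negative.

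A reader may also notice that, under protocol Section 6.12.3, ADA blood "will be collected in heparinised blood collection tubes" while the same sentence has serum assayed. That is a wording conflict within that section. It has no bearing on which ADA proportion is tabulated and should be reconciled as a separate item.

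**Conclusion.** Wrong as written. The protocol's secondary objective and endpoint concern positive ADA of any type; the SAP's definition, analysis section and only ADA tables cover a subset, and the SAP denies any departure. Executed literally, the plan leaves a stated secondary objective without a by-arm summary.

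The conclusion rests on the wording alone and needs no assumed rate. How much it would matter numerically is unknown: with an assumed neutralising share of 0% to 100%, the tabulated proportion is 0% to 100% of ADA incidence, so the shortfall may be nil. The primary efficacy analysis, the alpha control, the power and the secondary testing hierarchy are unaffected. This is a reporting correction worth making, not a threat to the trial's main conclusion.

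**What to change.** - **SAP 2.5.3 and 4.6.2:** define the endpoint as the proportion of subjects with confirmed positive ADA by Week 12 and by Week 16, among those with at least one post-baseline ADA result. State that confirmed positive is the reading given to the protocol's term, since the protocol does not define the tiers.
- **Tables 14.2.5.1A and B:** report that proportion by arm at each time point, show the number of subjects with a post-baseline ADA result, and keep neutralising ADA as a sub-row.
- **SAP 4.6.3:** use the same confirmed-positive definition for the ADA-positive group, so that its size agrees with the table in the same population.
- **SAP Section 5:** correct the statement. With the changes above, it should describe how the endpoint is made operational. If the sponsor prefers neutralising ADA as the sole endpoint, it should record and justify that departure.
- **Separately:** reconcile the tube type and assay matrix in protocol Section 6.12.3.

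The cost is a few lines of SAP text and added rows in an existing table shell. No new samples or visits are needed, because the SAP already assigns the screening, confirmatory and neutralising categories.

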#### 2.5.4. Safety Variables

Safety assessments performed during the study included physical examinations, measurement of vital signs, 12-lead electrocardiograms (ECGs), clinical laboratory evaluations including hematology, serum chemistry, and urinalysis, concomitant medications, and monitoring of AEs.

### **3. SUBJECT POPULATIONS**

#### **3.1. Population Definitions**

The following subject populations will be evaluated and used for presentation and analysis of the data:

Safety Population: all randomized subjects who received any amount of study drug.

Full Analysis Set (FAS): all randomized subjects who received any amount of study drug and who have results from baseline and from  $\geq 1$  post-baseline assessment will be included in the PD and efficacy analysis.

Per Protocol (PP) Population: all subjects in the FAS without any major protocol violations

Pharmacokinetic (PK) Population: all randomized subjects who receive a Day 0 dose of study drug and who have sufficient PK data for analysis (meeting the required minimum blood volume collected along with the sampling schedule, and sampling time, and without vomiting)

Subjects in the all populations will be included in the respective treatment groups on an as-treated basis.

The safety population will be used for safety analyses, demographic and other baseline subject characteristics, and the FAS and PP populations will be used for the primary, secondary, exploratory, PD, and immunogenicity endpoints. The FAS population will also be used for the Disposition by Study Visit tabulation. The PK population will be used for PK summaries.

If it is determined that a significant number of subjects were not treated as randomized, additional analyses on the subjects analyzed as randomized may be performed.

Of note, per the adaptive study design, the overrun subjects randomized in Stage 2 will be included in all analyses where data is available.

As noted in Section 2.1, subjects randomized during Stage 2 to a dose not studied in Stage 1 will be included in final analyses.

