6.2.3 Dose Preparation and Administration

Study drug (PTG-100 or placebo) will be administered by subjects orally QD.

Matching PTG-100 (150-mg or 300-mg capsule) and placebo capsules will be provided to subjects in prepackaged individual study drug wallet kits, identical in appearance, according to the randomisation schedule. Each prepackaged kit will be appropriately labelled. Each day during the double-blind treatment period (preferably in the morning), subjects will take a total of 3 capsules, without regard to meals, according to their blinded treatment assignment, as follows:

- 150 mg PTG-100 group will receive: 1 × 150-mg capsule, 2 × placebo capsules
- 300 mg PTG-100 group will receive: 2 × 150-mg capsules, 1 × placebo capsule
- 900 mg PTG-100 group will receive: 3 × 300-mg capsules
- Placebo group will receive: 3 × placebo capsules

Study drug will be prepared in blinded blister packs and dispensed by the pharmacist (or appropriate designee) at study site visits; the subject will return any unused study drug at site visits during which site personnel will record used and unused capsules.

Subjects will be encouraged to take their daily study drug in the morning at approximately the same time each day. If the subject forgets to take a morning dose, the subject will be advised to take the dose on the same day. If it has been more than 12 hours since they were due to take the dose, they will be advised to skip that dose and resume the daily schedule with the next dose. Subjects will be told to not “double-up” on the doses if doses are missed.

All study personnel including the Sponsor, Contract Research Organization (CRO), Medical Monitors, Investigator, site pharmacist (or designee), site personnel involved in

study conduct, and subjects will remain blinded to study medication assignment. Appropriate unit doses, as described above, will be administered to consecutively-numbered subjects.

For all site visit days, doses will be administered orally after PK and PD blood collections. Doses will be preceded by an overnight fast (ie, at least 8 hours) from food (not including water) on Days 0, 28, 84, and 112 only prior to safety lab collection. Subjects may resume food after the blood collection.

At all other times during the study, subjects will have no water or meal restrictions or requirements.

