#### 4.2.8. Missing, Unused, and Spurious Data

All data recorded on the CRF will be included in data listings that will accompany the clinical study report.

For the primary efficacy endpoint and other success/failure secondary endpoints, subjects who discontinue prior to Week 12 will be considered treatment failures, a worst-case scenario.

These endpoints include

- Clinical Remission (primary endpoint)
- Clinical Response
- Endoscopic Response
- Endoscopic Remission

A single sensitivity analysis on each of these endpoints will utilize the per protocol population (complete-case) in order to examine the robustness of the results.

For all continuous secondary endpoints, data will be analyzed using a mixed model repeated measures approach described in Section 4.6.2. The MMRM method assume that missing data arose from a missing at random (MAR) mechanism, i.e. the missing data is independent of unobserved data given the non-missing data. The MAR assumption is reasonable in clinical trials as the observed data explain much of the missingness in many scenarios, particularly in well controlled studies such as clinical trials, in which an extensive effort is made to observe all the outcomes and the factors that influence them. In MMRM, the information from the observed data is used via the within-patient correlation structure to provide information about unobserved data. The data from all visits are simultaneously analyzed using restricted maximum likelihood methods and no explicit imputation for missing values is performed. This method will be used in the testing of the secondary endpoints.

In addition, sensitivity analyses may be performed on complete datasets where missing data is imputed using the following methodology:

- LOCF (last observation carried forward)
- WOCF (missing data imputed using the worst observation observed prior to that time point)
- Per Protocol population (complete-case scenario- no imputation required)
- Multiple Imputation

For multiple imputation, two approaches may be used. In the first approach, for missing response data at various time points, the following steps are taken:

- Draw a random sample from the normal distribution with a mean and variance calculated from the non-missing responses at that time point
- Repeat this process five times to form five imputed complete datasets
- Fit the MMRM model to each imputed dataset to estimate the treatment effect on the response variable and the variance

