#### **4.6. Efficacy Evaluations**

##### **4.6.1. Primary Efficacy Analysis**

The primary efficacy endpoint for this study is the proportion of subjects receiving PTG-100 with clinical remission at Week 12 compared with placebo, as defined in Section 2.5.1.

Efficacy analysis for the primary endpoint will be conducted using the FAS population and will be repeated on the PP population as a sensitivity analysis.

The proportion of subjects with clinical remission at Week 12 will be calculated and reported with a two-sided 95% exact confidence interval as an estimate of the true proportion of subjects with clinical remission in the target patient population. Two approaches will be used to report the percentages:

Approach 1: The naïve percentage and associated 95% CI for each dose group, based on data combined across both stages of the trial.

Approach 2: For doses that are selected for Stage 2, the Stage 2-only proportion of subjects with clinical remission and 95% CI will be reported. For doses not selected for Stage 2, the proportions and associated 95% CI based on Stage 1 data only will be reported.

Analysis to examine treatment effect (i.e. odds ratio for clinical remission among subjects with each active dose vs. placebo and 95% CI) will be carried out at the Week 12 time point, employing a Cochran-Mantel-Haenszel test stratified for prior TNF- $\alpha$  use (yes/no). Raw p-values, unadjusted for multiple comparisons, associated with each odds ratio will also be presented.

To obtain the primary endpoint study p-values, Simes-adjusted p-values for each dose regimen vs. placebo that are produced for the primary endpoint from the first and second stages of the study will be combined by using the inverse normal combination function to obtain the final p-value.

The components contributing to the Stage 1 portion of the p-value will include data of subjects from all 4 original dose groups (placebo, low, medium, high dose) who were enrolled during Stage 1, defined as on or before the data snapshot date for the interim look at efficacy.

The components contributing to the Stage 2 portion of the p-value will be data from subjects from the dose groups that were not discontinued who were enrolled after the date of the data snapshot for the interim look at efficacy.

The final p-value for the trial primary endpoint will be a weighted combination of the two components, as described below.

The null hypothesis to be tested is

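### SAP 3.1 groups the FAS as treated for the primary efficacy test, and no committed analysis compares the arms as randomised

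*SAP*

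**What the plan says.** SAP 3.1 defines the Safety, FAS, PP and PK populations and then gives a single grouping rule: "Subjects in the all populations will be included in the respective treatment groups on an as-treated basis". The FAS is not excepted. On the primary endpoint, SAP 4.6.1 says: "Efficacy analysis for the primary endpoint will be conducted using the FAS population", with a repeat on the PP population. SAP 3.1 defines PP as "all subjects in the FAS without any major protocol violations", and SAP 4.2.8 makes it the one sensitivity analysis for each of the four binary endpoints. The efficacy tables listed in SAP 7.1 are for FAS and PP, apart from sensitivity tables for continuous endpoints that are produced only if needed.

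The only as-randomised provision is conditional and optional: "If it is determined that a significant number of subjects were not treated as randomized", then "additional analyses on the subjects analyzed as randomized may be performed". No threshold is given.

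The protocol's FAS definition (7.3 and the synopsis) gives no grouping rule either way, so as-treated grouping first appears in the SAP.

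**The concern.** Grouping subjects by assigned arm preserves the comparison that randomisation created. The stage-wise tests, the Simes adjustment and the inverse-normal combination in SAP 4.6.1 all take that comparison as their starting point. As-treated grouping is normal for safety and PK. For an efficacy test at one-sided 0.025 it gives up the randomised basis whenever a subject gets the wrong kit, and the SAP names no benefit in return.

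The rule is also incomplete. Protocol 6.2.3 says: "Study drug will be prepared in blinded blister packs and dispensed by the pharmacist (or appropriate designee) at study site visits". A subject could therefore receive the assigned kit at one visit and a different one at the next. The SAP does not say which group that subject belongs to, and two programmers could decide differently.

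**Working it through.** **The plan's own figures.** The plan gives no mis-treatment rate. The nearest figure is the power of 91% at N=240 (SAP Table 2, first scenario). An independent simulation of the design (Stage 1 of 60, two doses kept, 75 per arm, no overrun) gave 90.8%; the second scenario gave 82.1% against 82% stated. With about 60 overrun subjects in four arms, the first-scenario power is 88.1% to 88.7% across Stage 1 sizes of 60 and 80 with two doses kept. That is a separate matter. None of these figures depends on the grouping rule.

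**Step 1: the text.** All populations are as treated (SAP 3.1). The primary test is on the FAS (SAP 4.6.1). PP is a subset of the FAS (SAP 3.1) and the only sensitivity set for the binary endpoints (SAP 4.2.8). The as-randomised analysis is optional (SAP 3.1). So no analysis by randomised arm is guaranteed.

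**Step 2: one mis-treated subject.** The counts are assumed, chosen near the planning rates of about 10% and 31% (SAP 4.1) so that the as-randomised difference is 20.0 points. One placebo-randomised subject received active drug. With n per arm, a remitters on active and c on placebo, as-treated grouping gives:

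- subject remitted: (a+1)/(n+1) − (c−1)/(n−1)
- subject did not remit: a/(n+1) − c/(n−1)

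| n per arm | As randomised | Remitter moved | Non-remitter moved |
|---|---|---|---|
| 75 | 23/75 − 8/75 = 20.0 | 24/76 − 7/74 = 22.1 (+2.1) | 23/76 − 8/74 = 19.5 (−0.5) |
| 35 | 11/35 − 4/35 = 20.0 | 12/36 − 3/34 = 24.5 (+4.5) | 11/36 − 4/34 = 18.8 (−1.2) |
| 30 | 9/30 − 3/30 = 20.0 | 10/31 − 2/29 = 25.4 (+5.4) | 9/31 − 3/29 = 18.7 (−1.3) |
| 20 | 6/20 − 2/20 = 20.0 | 7/21 − 1/19 = 28.1 (+8.1) | 6/21 − 2/19 = 18.0 (−2.0) |
| 15 | 5/15 − 2/15 = 20.0 | 6/16 − 1/14 = 30.4 (+10.4) | 5/16 − 2/14 = 17.0 (−3.0) |

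The row of 75 is the middle of the planned 70 to 80 per selected arm (SAP 2.1). The other rows are Stage 1 on two readings:

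- If Stage 1 is the 60 to 80 interim subjects (SAP 2.1), there are 15 to 20 per arm.
- If Stage 1 is everyone enrolled up to the data snapshot (SAP 4.6.1) and the roughly 60 overrun subjects fall before it, the total is 120 to 140, or 30 to 35 per arm.

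The opposite error, one active-randomised subject who received placebo, reverses the signs. At 75 per arm, a remitter gives 22/74 − 9/76 = 17.9 and a non-remitter gives 23/74 − 8/76 = 20.6. The direction therefore cannot be known in advance.

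**Step 3: the cost of as-randomised grouping.** Suppose a fraction m of each arm receives the other treatment, unrelated to prognosis. The as-treated difference stays at 21 points and the as-randomised difference is 21 × (1 − 2m):

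- m = 1%: 20.58 points (gap 0.42)
- m = 2%: 20.16 points (gap 0.84)

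Power for a simple two-group comparison at 75 per arm, one-sided 0.025, falls from 89.8% with no swaps to 88.5% and 87.2%. These values of m are assumptions.

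**The case against.** The strongest reply is that the rule does nothing unless dosing goes wrong. Allocation is by IXRS (Protocol 4.1) and kits are blinded and prepackaged (Protocol 6.2.3), so errors should be rare. The protocol sets no grouping rule, so nothing in it is contradicted. Protocol violations and dosing are listed by subject (SAP 3.2 and 7.2), so an error would not be hidden. If the sponsor judged a wrong-kit subject a major violation, PP would drop that subject, and comparing FAS with PP would show the influence.

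This argument limits the size and stands to that extent. It does not defend the rule. PP exclusion is at the sponsor's discretion (SAP 3.2), and PP still yields no result by randomised arm in the full set. If errors are rare, as-randomised grouping costs almost nothing.

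Three stronger readings are tempting, and the documents do not support them:

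- **That the primary result will be biased, or biased towards the drug.** No error rate is given, and Step 2 shows shifts both ways. One moved subject can cross 0.025 on borderline counts: 17/75 against 8/75 gives one-sided p = 0.024, and moving one active remitter to placebo (16/74 against 9/76) gives 0.054. But those counts are hand-picked, and the test is a single unstratified comparison without the Simes and stage combination.
- **That 8 to 10 points is the Stage 1 shift.** This holds only for a remitter at 15 to 20 per arm. On the snapshot-date reading it is about half that. In either case the Stage 1 p-value is Simes-adjusted and combined with Stage 2.
- **That FAS entry removes many early dropouts.** The qualifying post-baseline assessment is not named. If Day 0 post-dose checks count, almost nobody is lost. The narrow reading rests on wording about a disposition table (SAP 4.4), and subjects complete a diary daily (Protocol 6.11.1). One lost non-remitter at 75 per arm adds 31 × 75/74 − 31 = 0.4 points to a 31% rate and 10 × 75/74 − 10 = 0.1 to a 10% rate.

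**Conclusion.** The point holds as a defect in a stated rule and should be fixed. The primary efficacy analysis and its only planned sensitivity analysis both group subjects by treatment received, and an as-randomised result depends on an undefined trigger and on discretion.

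The expected effect is probably small and its direction unknown. For one mis-treated subject it is about 0.5 to 2 points on the final difference at 75 per arm, and more within Stage 1, depending on how Stage 1 is defined. These sizes rest on assumed counts and an assumed single error, because the documents give neither a mis-treatment rate nor a basis for one. The stated sample size and power are unaffected.

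**What to change.** In SAP 3.1:

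- State that efficacy endpoints in the FAS are analysed by the arm to which subjects were randomised. PP, as a subset, should follow. PD and immunogenicity endpoints also use these sets, so say which rule covers them.
- Keep as-treated grouping for the Safety and PK populations, and state how a subject who received more than one treatment is grouped.
- Delete the sentence that makes the as-randomised analysis optional.

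The cost is a few sentences, with no new data and no change in N. The downside is slight dilution from any mis-treated subject, as in Step 3.

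Optional and separate: SAP 4.2.8 says "subjects who discontinue prior to Week 12 will be considered treatment failures, a worst-case scenario". The SAP could add that a dosed subject who discontinues before Week 12 stays in the denominator as a failure for the four binary endpoints listed there, even with no post-baseline result. This costs more. It departs from the protocol FAS definition, so it needs an entry in SAP 5 and matching edits in SAP 4.6.1, 4.6.2 and the FAS table titles. Its effect is small, and the main fix does not depend on it.
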